## 16.9. Sample Size and Power Considerations

For OS, a 61.3% improvement in median survival from randomization, from 3 years for placebo to 4.83 years on lenalidomide is considered clinically relevant. The OS is assumed to be exponential with a constant failure (hazard) rate. When the total number of events is approximately 160 over both treatment arms, then a two-sided log-rank test with an overall significance level of 0.025 (allowing for one interim analysis) would have 80% power to detect a hazard rate ratio of 0.62 (that is, if the survival curves are exponential, to detect a 61.3% difference in the median OS in the 2 arms). To ensure timely completion of the study, 320 subjects will be enrolled, 160 in each treatment arm. Enrollment will close once 320 subjects are randomized or 160 adjudicated PFS events are reached, whichever comes first.

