#### **Analysis and Reporting:**

The final analysis on OS will be performed and reported when 160 subjects have died (ie, when full information necessary to have 80% power for OS is achieved).

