## 16. STATISTICAL ANALYSES

### 16.1. Statistical Overview

The objective of the statistical analysis will be to compare the efficacy and safety of lenalidomide versus placebo as maintenance therapy in subjects with relapsed or refractory B-cell chronic lymphocytic leukemia (CLL) having achieved PR or better after second-line therapy.

Overall survival (OS) will be the primary endpoint for the protocol following amendment #10. This analysis will be performed at the completion of the study. It is estimated that at least 160 subjects across both treatment arms have died at the time of analysis (yielding 80% power to detect a 61.3% improvement in median OS for a two-sided test at 0.025 level allowing for one interim analysis).

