### **16.3.3. Efficacy Analyses**

Kaplan-Meier product limit methods will be used to estimate the survivorship functions for the time-to-event endpoints (eg, OS, and PFS2). A two-sided log-rank test stratified by the 3 strata used in the randomization will be used as the primary analytic method to compare survivorship functions for time-to-event variables in the 2 treatment groups. In terms of the survivorship functions for each treatment group, the hypotheses of interest were:

$$H_0: F_A(t) = F_P(t) \text{ for all } t$$

Versus

$$H_1: F_P(t) \neq F_A(t) \text{ for all } t$$

where  $F_P$  is the survivorship function for placebo and  $F_A$  is the survivorship function for lenalidomide.

Median OS will be estimated using Kaplan-Meier estimates, and the 95% confidence intervals (CI) will be computed using the method of Brookmeyer and Crowley. Hazard ratio will be calculated using Cox model stratified for the 3 strata (ie, response to second-line induction chemotherapy, age, and presence of at least one prognostic factor) to account for the stratified randomization. The Cox model will also be used to identify prognostic factors.

Cross-tabulations will be provided by treatment group to summarize improvements from the best response during induction therapy.

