6. GENERAL STATISTICAL CONSIDERATIONS

6.1. Sample Size

For OS, a 61.3% improvement in median survival from randomization, from 3 years for placebo to 4.84 years on lenalidomide is considered clinically relevant. For PFS, a 61.3% improvement in median time to progression from randomization, from 20 months for placebo to 32.3 months on lenalidomide is considered clinically relevant. The OS and PFS distributions are assumed to be exponential with a constant failure (hazard) rate. When the total number of events is approximately 160 over both treatment arms, then a two-sided log-rank test with an overall significance level of 0.025 (allowing for the co-primary endpoints) would have 80% power to detect a hazard rate ratio of 0.62. To ensure timely completion of the study, 320 subjects will be enrolled, 160 in each treatment arm.

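### At 160 deaths the plan's own inputs give about 78% power for a hazard ratio of 0.62; the stated 80% needs about 168 deaths

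*Protocol*

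**What the plan says.** Protocol 16.9 sets the overall survival (OS) design. It assumes exponential survival, 1:1 allocation of 320 subjects and a "two-sided log-rank test with an overall significance level of 0.025 (allowing for one interim analysis"). "When the total number of events is approximately 160 over both treatment arms", that test "would have 80% power to detect a hazard rate ratio of 0.62". The medians run "from 3 years for placebo to 4.83 years on lenalidomide is considered clinically relevant" in Protocol 16.9; the SAP has "from 3 years for placebo to 4.84 years on lenalidomide is considered clinically relevant", and the protocol synopsis agrees with the SAP.

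The event count is worded differently from place to place:

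- Protocol synopsis, Analysis and Reporting: the final OS analysis takes place "when 160 subjects have died (ie, when full information necessary to have 80% power for OS is achieved"). The count carries no qualifier.
- Protocol 16.1: the analysis is at study completion, with an estimate of at least 160 deaths, "yielding 80% power to detect a 61.3% improvement in median OS for a two-sided test at 0.025 level".
- Protocol 16.9 and SAP 6.1: approximately 160 events.
- SAP 11: the OS comparison is run at 160 deaths or more.
- SAP 14.2: an interim at about 60% information and the final analysis at 100% information, set at 160 deaths, with O'Brien-Fleming-type spending of a two-sided 0.025.

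The primary test in Protocol 16.3.3 is "A two-sided log-rank test stratified by the 3 strata used in the randomization". Neither document names the power formula or says whether stratification was allowed for.

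**The concern.** The stated inputs (hazard ratio, alpha, sidedness, allocation and number of deaths) fix the power almost completely, so the 80% can be checked. It comes out a little low, and every standard formula tried errs in the same direction.

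Under Protocol 16.1, OS has been the primary endpoint since Amendment 10. The 160-death trigger and the reading of a non-significant result both lean on this power figure. The synopsis goes furthest: it presents 160 deaths as the count at which 80% power is secured.

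**Working it through.** **Inputs.** Deaths d = 160; hazard ratio 0.62; two-sided alpha 0.025; 1:1 allocation (Protocol 16.9, SAP 6.1). Interim at 60% information with O'Brien-Fleming-type spending (SAP 14.2). Then z(0.9875) = 2.2414, z(0.80) = 0.8416 and |ln 0.62| = 0.4780.

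**1. Schoenfeld, fixed design (closest to the plan's 80%).**
Power = Φ(|ln HR|·√d/2 − 2.2414) = Φ(0.4780 × 12.649/2 − 2.2414) = Φ(3.0234 − 2.2414) = Φ(0.7820) = **78.3%**.
Deaths for 80% = 4 × (2.2414 + 0.8416)² / 0.4780² = 166.4, so **167**.

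**2. Effect of the medians.** 3/4.84 gives HR 0.6198 and 78.3%. 3/4.83 gives HR 0.6211 and 78.0%, with 168 deaths for 80%. The difference in the second decimal of the median does not explain the gap.

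**3. With the interim.** The SAP's boundary table is blacked out, so I used the Lan-DeMets O'Brien-Fleming spending function at 60% information. The critical values are z = 3.020 and then 2.254 (nominal two-sided p = 0.0025 and 0.0242). Power at 160 deaths is **78.1%**. Deaths for 80% are 167.2, so **168**. The interim costs only about 0.2 points.

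**4. Freedman.** (1 − 0.62)/(1 + 0.62) = 0.23457.
Power = Φ(0.23457 × 12.649 − 2.2414) = Φ(0.7257) = **76.6%**.
Deaths for 80% = (3.0830/0.23457)² = 172.7, so **173**.

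**5. What 160 deaths do support.** HR = exp(−2 × 3.0830/12.649) = **0.614** at 80% power.

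| Method | Power at 160 deaths | Deaths for 80% |
|---|---|---|
| Schoenfeld, fixed | 78.3% | 167 |
| Schoenfeld with interim at 60% | 78.1% | 168 |
| Freedman, fixed | 76.6% | 173 |

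**6. If more than 160 deaths are analysed.** Take the plan's exponential medians, 320 subjects and 5 years of follow-up after the last randomization. Accrual time and loss to follow-up are not given. With assumed uniform accrual over 2 to 6 years and no loss, 212 to 240 deaths are expected, and Schoenfeld power is 89% to 93%. Early closure of enrolment, which Protocol 16.9 allows, would lower these counts.

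**7. Sensitivity for the stratified test.** The strata form up to 2 × 2 × 3 = 12 cells. Their sizes and prognostic strength are not given. The stratified group-sequential test was simulated at 160 deaths, with an interim at 96, under these assumptions: 5-year uniform accrual; permuted blocks of 4; MRD-negative complete response in 3% to 50% of subjects; age over 70 in 25% to 50%; poor-prognosis Yes/No/Unknown shares from 80/15/5 to 33/33/33. Power was 75.4% to 76.5%. In the one scenario with prognostic strata, the stratified test had more power than the unstratified one (75.7% against 73.6%).

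**The case against.** The best defence is that the gap is of rounding size. Protocol 16.9 and SAP 6.1 say approximately 160, no formula is named, and 78.3% is within two points of 80%. That stands as a limit on size: 160 is 7 deaths short of 167, about 4%. It does not cover the synopsis line, which is unqualified and says that 160 deaths secure 80%.

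The second defence is that the analysis may come later. Protocol 16.1 and SAP 11 allow 160 deaths or more, and SAP 5.1 continues follow-up to the later of 5 years and at least 160 deaths. On the assumptions in step 6, power would then exceed 80%. This also stands. A reader might infer that the trial as run has a 22% to 25% chance of missing a hazard ratio of 0.62. The documents do not support that as a general statement, because it holds only for an analysis at exactly 160 deaths, and the upper end also needs the simulation's assumptions. Even so, a later analysis does not make the figure attached to 160 deaths right.

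A reader might also take 75% to 76% as the true power of the planned test and blame the interim and the stratification. The documents give no stratum shares, accrual pattern or block size, so that figure cannot be derived from them. The interim accounts for almost none of the drop. Powering a stratified log-rank test with an unstratified formula is common practice, not an arithmetic error, and stratification can raise power when the factors are prognostic.

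**Conclusion.** The point holds as a modest arithmetic correction. On the plan's own inputs, 160 deaths give about 78% power for a hazard ratio of 0.62 at two-sided 0.025. About 167 to 168 deaths are needed for 80% by Schoenfeld, or 173 by Freedman. The Schoenfeld figures rest only on stated inputs, proportional hazards and, for the interim, the Lan-DeMets form of the spending function. The synopsis statement that 160 deaths is the full information for 80% power is therefore wrong, while the approximate wording elsewhere is only slightly optimistic.

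Nothing here shows that the trial is underpowered in any serious sense. Stratification may bring power at 160 deaths to about 75% to 77%, but that is a sensitivity range under assumed inputs.

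**What to change.** - In Protocol 16.1 and 16.9 and SAP 6.1, restate the power as about 78% at 160 deaths. Alternatively, keep 80% and give about 168 deaths as the matching count; SAP 14.2 and the synopsis would then need the same count.
- In the protocol synopsis, delete the statement that 160 deaths is the full information for 80% power.
- Name the formula or software used, and say whether the interim and the stratification were allowed for.
- If the sponsor wants to show the effect of stratification, give it as a sensitivity range with its assumptions listed, not as the design power.

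The first option costs wording only, and the stated power becomes slightly less favourable. The second means waiting for about 8 more deaths if the analysis is triggered by count. Neither needs extra patients or a change to the test or alpha.

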## **17. QUALITY CONTROL AND QUALITY ASSURANCE**

### **17.1. Monitoring**

Celgene ensures that appropriate monitoring procedures are performed before, during and after the study. Before the study is initiated at a site visit or at an investigator meeting, all aspects of the study are reviewed with the investigator(s) and the staff. Prior to enrolling subjects into the study, a Celgene representative will review the protocol, CRFs, procedures for obtaining informed consent, record keeping, and reporting of AEs with the Investigator(s). Monitoring will include on-site visits with the Investigator(s) and his/her staff as well as any appropriate communications by mail, fax, or telephone. At each monitoring visit, the facilities, study drug storage area, CRFs, subject's source documents, and all other study documentation will be inspected/reviewed by the Celgene representative for adherence to the protocol and Good Clinical Practice.

The monitor will review CRFs for completion and accuracy. Accuracy will be checked by performing source data verification at each site visit that is a direct comparison of the entries made onto the CRF against the appropriate source documentation. Any resulting discrepancies will be reviewed with the Investigator(s) and/or his/her staff. Any necessary corrections will be made directly to the CRFs or via queries by the Investigator(s) and/or his/her staff. Monitoring procedures require that informed consents, adherence to inclusion/exclusion criteria, and documentation of SAEs and the proper recording be verified. Additional monitoring activities may be outlined in a study-specific monitoring plan.

### **17.2. Audits and Inspections**

In addition to the routine monitoring procedures, a Good Clinical Practice Quality Assurance unit exists within Celgene. From time to time, representatives of this unit will conduct audits of clinical research activities in accordance with Celgene standard operating procedures (SOPs) to evaluate compliance with Good Clinical Practice guidelines and regulations.

The Investigator(s) is required to permit direct access to the facilities where the study took place, source documents, CRFs, and applicable supporting records of subject participation for audits and inspections by Institutional Review Board/Independent Ethic Committees (IRB/IECs), regulatory authorities (eg, FDA, EMA, Health Canada) and company authorized representatives. The Investigator(s) should make every effort to be available for the audits and/or inspections. If the Investigator(s) is contacted by any regulatory authority regarding an inspection, he/she should contact Celgene immediately.

### **17.3. Investigator(s) Responsibilities**

Investigator responsibilities are set out in the International Conference on Harmonisation (ICH) guideline for Good Clinical Practice and in the US Code of Federal Regulations. Celgene or a representative will contact and select all principal investigators or co-investigators who in turn will select their staff. The investigator must give the monitor access to relevant records to confirm the above.

The Investigator(s) is responsible for keeping a record of all subjects who sign an Informed Consent Form and are screened for entry into the study. For those subjects who fail screening, the reason(s) for exclusion must be recorded in the subject's source documents and in the IVRS system.

No procedure/assessment/measurement/test other than those outlined here, or in the schedule of study assessments, is to be performed without the prior written approval of Celgene, or unless deemed by the investigator(s) as necessary for the subject's medical care. Investigator(s) and/or authorized designee(s) must enter study data onto CRFs supplied by Celgene. The data on the CRF will be recorded in an anonymous manner to protect the subject's identity by using a unique identifier that will prevent personal identifiable information.

The Investigator(s), or a designated member of the Investigators' staff, must be available at some time during monitoring visits to review data and resolve any queries and to allow direct access to the subject's records (eg, medical records, office charts, hospital charts, and study related charts) for source data verification. The CRFs must be completed as soon as possible after the subject's visit but no later than prior to each monitoring visit and be made available to the Celgene representative(s) so that the accuracy and completeness may be checked.

## **18. REGULATORY CONSIDERATIONS**

### **18.1. Institutional Review Board/Independent Ethics Committee Review and Approval**

The protocol for this study has been designed in accordance with the general ethical principles outlined in the Declaration of Helsinki ([Appendix 22.2](#)). The review of this protocol by the IRB/IEC and the performance of all aspects of the study, including the methods used for obtaining informed consent, must also be in accordance with principles enunciated in the declaration, as well as ICH Guidelines, Title 21 of the Code of Federal Regulations (CFR), Part 50 Protection of Human Patients and Part 56 Institutional Review Boards. Before implementing this study, the protocol, the proposed informed consent form and other information to subjects, must be reviewed by a properly constituted Institutional Review Board/Independent Ethics Committee (IRB/IEC). A signed and dated statement that the protocol and informed consent have been approved by the IRB/IEC must be given to Celgene before the study initiation. The names and occupations of the chairman and the members of the IRB/IEC must be supplied to Celgene.

The Investigator(s) will be responsible for preparing documents for submission to the relevant IRB/IEC and obtaining written approval for this study. The approval will be obtained prior to the initiation of the study.

A copy of the IRB/IEC approval for the protocol and the Informed Consent is to be provided to Celgene. The approval for both the protocol and informed consent must specify the date of approval, protocol number and version, or amendment number.

The Investigator(s) is responsible for notifying the IRB/IEC of any serious deviations from the protocol, or anything else that may involve added risk to subjects.

Any advertisements used to recruit subjects for the study must be reviewed and approved by Celgene and the IRB/IEC prior to use.

### **18.2. Protocol Amendments**

Any amendment to this protocol that seems appropriate, as the study progresses (eg, affects safety or efficacy) will be agreed upon between the coordinating and/or principal investigator(s) and the Celgene study physician. Amendments will be submitted to the IRB/IEC for written approval before the implementation of the amended version. The written signed approval from the IRB/IEC should refer specifically to the investigator(s) and to the protocol number and title and mention any amendment numbers that are applicable. Celgene does not require that amendments that are administrative in nature receive IRB/IEC approval, but will be submitted to the IRB/IEC for information purposes. If local IRB/IEC procedures require approval of administrative amendments, then study sites should follow local IRB/IEC regulations.

### **18.3. Informed Consent**

The Investigator(s) must obtain informed consent of a subject or his/her designee prior to any study related procedures as per Good Clinical Practices (GCP) as set forth in the 21 CFR Parts 50 and 56 and ICH guidelines.

Documentation that informed consent occurred prior to the subject's entry into the study and of the informed consent process should be recorded in the subject's source documents. The original consent form, signed and dated by the subject and by the person consenting the subject prior to the subject's entry into the study, must be maintained in the Investigator's study files and a copy given to the subject. In addition, if a protocol is amended and it impacts on the content of the informed consent, the informed consent must be revised. Subjects participating in the study when the amended protocol is implemented must be re-consented with the revised version of the informed consent. The revised consent form signed and dated by the subject and by the person consenting the subject must be maintained in the Investigator's study files and a copy given to the subject.

#### **18.4. Patient Confidentiality**

Celgene affirms the patient's right to protection against invasion of privacy. In compliance with United States federal regulations, Celgene requires the Investigator(s) to permit Celgene's representatives and, when necessary, representatives of the FDA or other regulatory authorities to review and/or copy any medical records relevant to the study in accordance with local laws.

Should direct access to medical records require a waiver or authorization separate from the patient's statement of informed consent, it is the responsibility of the Investigator(s) to obtain such permission in writing from the appropriate individual.

## **19. DATA HANDLING AND RECORDKEEPING**

### **19.1. Data/Documents**

The investigator(s) must ensure that the records and documents pertaining to the conduct of the study and the distribution of the study drug, CRFs, source documents, original documents, data, records (eg, hospital records; clinical and office charts; laboratory notes; memoranda; patient's diaries or evaluation checklists; pharmacy dispensing records; recorded data from automated instruments; copies or transcriptions certified after verification as being accurate copies; microfiches; photographic negatives, microfilm, or magnetic media; x-rays; patient files), and records kept at the pharmacy, at the laboratories, and at medico-technical departments involved in the clinical study are complete, accurate, filed and retained.

### **19.2. Data Management**

Data will be entered into the clinical database as per Celgene SOPs. These data will be electronically verified through use of on-line checks during data entry, and through programmed edit checks specified by the clinical team. Discrepancies in the data will be brought to the attention of the clinical team, and investigational site personnel, if necessary, in the form of a Data Clarification Form (DCF). Resolutions to these issues will be reflected in the database. An audit trail within the system will track all changes made to the data. A quality control audit will be performed per Celgene SOP(s).

### **19.3. Retention of Records**

The investigator(s) must maintain records of all study documents and supporting information relating to the conduct of the study. This documentation includes, but is not limited to, protocols, case report forms, advertising for subject participation, adverse event reports, subject source data, correspondence with health authorities and IRBs/IECs, informed consent forms, investigator(s) curricula vitae, monitoring visit logs, laboratory reference ranges, laboratory certification or quality control procedures, and laboratory director curriculum vitae. Subject files and other source data must be kept for the maximum period of time permitted by the hospital, institution or private practice specified below. The study monitor must be consulted if the investigator(s) wishes to assign the study files to someone else, remove them to another location or is unable to retain them for a specified period.

For studies conducted in the United States under a US Investigational New Drug (IND), the investigator(s) must retain the study records for a minimum of 2 years after a marketing application for the indication is approved or for 2 years after the IND is withdrawn. If no application is filed, or if the application is not approved for the indication, the records are to be retained for two years after the investigation (ie, the IND) is discontinued, and FDA is notified of that fact. For IND studies conducted outside the US, the investigator(s), must retain study records for the time period described above or according to local laws or requirements, whichever is longer. The monitor will inform the investigator(s) of the dates for retention. All study documents should be made available if required by relevant health authorities. For studies not conducted under the US IND, the investigator(s) records must be retained until at least 2 years after the last approval of a marketing application in an ICH region and until there are no

pending or contemplated marketing applications in an ICH region or at least 2 years have elapsed since the formal discontinuation of clinical development of the investigational product. These documents should be retained for a longer period if required by other applicable regulatory requirements.

